13.3. Other efficacy

Nadir for LogMAR BCVA and for LogCS

Nadir of BCVA/LogCS is defined for each eye of each subject as the worst value observed from baseline to the post-treatment timepoint of interest, including baseline and the post-treatment timepoint values.

For LogCS only, if there is at least one value off-chart between baseline and timepoint, then Nadir cannot be calculated as no off-chart value exists; off-chart LogCS will be imputed a value of 0.

If there are more than one off-chart value from baseline to the timepoint of interest, then the first value over time will be considered the nadir. If there is more than one worst value from baseline to the point of interest (i.e. identical worst values occurring more than once), then the first value over time will be considered the nadir.

The change from Nadir BCVA/LogCS will be calculated for each eye of each subject and will be analyzed as primary endpoint (see section 13.1.4).

The time to Nadir BCVA/LogCS will be calculated for each eye of each subject and will be expressed in Weeks. This analysis will be only descriptive.

Clinically Relevant Recovery (CRR)

At the eye level, a CRR from baseline is defined as:

- For eyes on-chart at baseline, an improvement of at least -0.2 LogMAR
- For eyes off-chart at baseline, eyes which became on-chart.

On-chart value is defined as \leq LogMAR 1.6

Subject with CRR from baseline is defined as subject with a CRR in at least one eye: Subject with at least one eye which was on chart at baseline, and which had an improvement of at least -0.2 LogMAR from baseline, or which was off-chart at baseline but became on-chart.

Subjects with CRR from baseline will be assessed for all subjects, bilaterally GS010 treated subjects and unilaterally GS010 treated subjects.

At the eye level, a CRR from nadir is defined as:

- For eyes on-chart at nadir, an improvement of at least -0.2 LogMAR from nadir
- For eyes off-chart at nadir, eyes which became on-chart.

Subject with CRR from nadir is defined as subject with a CRR in at least one eye: Subject with at least one eye which was on chart at nadir, and which had an improvement of at least -0.2 LogMAR from nadir, or which was off-chart at nadir but became on-chart.

Subjects with CRR from nadir will be assessed for all subjects, bilaterally GS010 treated subjects and unilaterally GS010 treated subjects.

These responder endpoints will be analyzed as section 13.2.3

Other responses parameters

Following responder endpoints will be analyzed as section 13.2.3:

- Eyes/subjects whose LogMAR BCVA improves (i.e. decrease) by ≥ 0.2 LogMAR (equivalent to a gain of ≥ 10 ETDRS letters) compared to baseline, i.e. an eye/subject is responder if:
LogMAR at the timepoint of interest - LogMAR at Baseline ≤ -0.20
- Eyes/subjects whose LogMAR BCVA improves (i.e. decrease) by ≥ 0.3 LogMAR (equivalent to a gain of ≥ 15 ETDRS letters) compared to baseline, i.e. an eye/subject is responder if:
LogMAR at the timepoint of interest - LogMAR at Baseline ≤ -0.30
- Eyes/subjects whose LogMAR BCVA improves (i.e. decrease) by ≥ 0.3 LogMAR (equivalent to a gain of ≥ 15 ETDRS letters) compared to nadir, i.e. an eye/subject is responder if:
LogMAR at the timepoint of interest - LogMAR at Nadir ≤ -0.30
- Eyes/subjects whose LogMAR visual acuity is ≤ 1.0 (i.e. equal or better than LogMAR 1.0, equivalent to equal or better than Snellen acuity of 20/200).
- Eyes/subjects whose LogMAR visual acuity is < 1.0 (i.e. better than LogMAR 1.0, equivalent to better than Snellen acuity of 20/200).
- Eyes/subjects whose LogMAR visual acuity is ≤ 1.6 (i.e. equal or better than LogMAR 1.6, equivalent to equal or better than Snellen acuity of 20/800).

- Eyes/subjects whose LogCS improves by ≥ 0.2 LogCS compared to baseline, i.e. an eye/subject is responder if:
LogCS at the timepoint of interest - LogCS at Baseline ≥ 0.20 .
- Eyes/subjects whose LogCS improves by ≥ 0.3 LogCS compared to baseline, i.e. an eye/subject is responder if:
LogCS at the timepoint of interest - LogCS at Baseline ≥ 0.30 .
- Eyes/subjects whose LogCS improves by ≥ 0.3 LogCS compared to nadir LogCS, i.e. an eye is responder if:
LogCS at the timepoint of interest - LogCS at Nadir ≥ 0.30 .

On-chart/off-chart BCVA and LogCS

Shift table and Mac Nemar test between Eyes on-chart/off-chart for BCVA/LogCS at baseline and Eyes on-chart/off-chart for LogMAR BCVA/LogCS at each timepoint (1.5, 2, 3, 4, 5 years) in each eye group will be performed.

Shift tables: Off-chart BCVA eyes at baseline moving to on-chart BCVA; On-chart BCVA eyes at baseline stay on-chart BCVA; Off-chart LogCS eyes at baseline moving to on-chart LogCS; On-chart LogCS at baseline stay on-chart LogCS

Exploratory efficacy

- Primary and secondary analyses will be repeated for the first affected eyes as exploratory efficacy analyses.

14.Safety outcomes

All outputs for safety outcomes will be based on the safety population. Period up to 1.5 year (0-1.5 year) and up to 5 years (0-5 years) will be presented separately.

Adverse events will be summarized as outlined above, permitting an assessment of change over the 5 years of follow-up. Other safety endpoints will be summarized as outlined above, showing change from baseline, for continuous endpoints.

There will be no statistical comparisons of the two treatment groups with respect to safety, unless otherwise specified within the relevant section.

If the second affected eye did not receive the correct treatment (as set in the randomization scheme) then the subject will be assigned to the arm corresponding to the treatment actually received. In case of assignment error, the treatment prevails over the order of affection of eye (i.e. first or second-affected/not- yet-affected eye corresponding to secondary or primary eye, respectively).

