### 16.2 Sample Size

Sample size calculation is based on the primary endpoint which is the change from baseline to 1.5 years post-treatment of the visual acuity (LogMAR). Masked preliminary data of the Phase III RESCUE and REVERSE sham-controlled studies of GS010 and monitored data from the Phase I/IIa safety and tolerability study of GS010 are used to estimate the standard deviation of the change from baseline to each available visit. These data do not take into account a potential treatment effect in the RESCUE and REVERSE studies and if there is an effect the standard deviation may be over-estimated.

From this masked preliminary analysis, a SD of 0.55 LogMAR has been estimated for the LogMAR change from baseline; this is reduced to 0.50 with the inclusion of baseline LogMAR as a covariate. Using this reduced value for SD and a treatment effect of 0.3 LogMAR in the change from baseline, the requested sample size to reach a power of 80% ( $\alpha = 0.05$  two-sided) according to an ANCOVA model including the baseline LogMAR value as covariate has been estimated, using SAS PROC POWER, to be 45 evaluable subjects per treatment group (i.e. 90 subjects in total).

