#### *16.4.1.5 Primary Individual Response*

The primary individual response of interest is the change from baseline to 1.5-Year post-treatment. A negative change from baseline in LogMAR is an improvement and a positive change from baseline is a worsening.

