13.1.4. Primary analysis of primary efficacy variable(s)

The primary analysis will be performed on the ITT population on the planned treatment (as randomized). The primary endpoint is the change from baseline of the BCVA, reported in LogMAR at 1.5 years post-treatment. Descriptive statistics will be presented for the baseline and 1.5 years post-treatment timepoints as well as for the change from baseline to the 1.5 years post-treatment based on data after imputation.

The treatment difference will be assessed with an ANCOVA model which includes terms to adjust for the baseline LogMAR value and includes treatment group as a fixed effect.

The analysis will be performed using a significance level of 0.05 (two-sided).

SAS code:

ARM =subject Treatment arm; change=Logmar change from baseline of second-affected/not-yet-affected eyes; Logmar0=Logmar at baseline

```
proc mixed data=XXX_;
class ARM;
model change=ARM logmar0 /s CL;
estimate " GS010 arm vs Placebo arm" ARM -1 1;
run;
```

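### Change from nadir is tested between arms against a worst value that treatment itself can move, so preventing loss earns no credit and can score worse than placebo if placebo eyes partly recover

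*SAP*

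**What the plan says.** SAP 13.3 defines nadir, for each eye, as "the worst value observed from baseline to the post-treatment timepoint of interest, including baseline and the post-treatment timepoint values". It then says: "The change from Nadir BCVA/LogCS will be calculated for each eye of each subject and will be analyzed as primary endpoint", with a reference to SAP 13.1.4. That section is the primary between-arm model: "The treatment difference will be assessed with an ANCOVA model which includes terms to adjust for the baseline LogMAR value and includes treatment group", tested at two-sided 0.05. The next paragraph of 13.3 makes time to nadir descriptive only, so the between-arm test on change from nadir appears to be deliberate.

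Nadir is also the reference for several responder measures in 13.3: clinically relevant recovery (CRR) from nadir, and gains of at least 0.3 LogMAR or 0.3 LogCS from nadir. The LogMAR responder is built on "LogMAR at the timepoint of interest - LogMAR at Nadir". All of these go to the logistic models by arm in SAP 13.2.3.

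On scale direction, Protocol 16.4.1.5 says: "A negative change from baseline in LogMAR is an improvement and a positive change from baseline is a worsening". SAP 6.3 spends all the alpha on the primary endpoint and leaves the other analyses without multiplicity adjustment.

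**The concern.** The primary ANCOVA is sound because baseline is fixed before randomisation. Nadir is not: it is an extreme taken over follow-up, and an effective treatment should make it shallower. Subtracting it removes part of the treatment effect from the outcome, and adjusting for baseline LogMAR cannot put that part back, because the distortion arises after baseline.

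Change from nadir in LogMAR cannot be positive. An eye that never loses vision and never gains any scores 0, the worst score available. The primary eye may be not yet affected at entry (Protocol 9.1), so loss after randomisation, and its prevention, are real possibilities here. A reader shown an ANCOVA p-value for change from nadir could take it as evidence for or against GS010 when it is not a clean measure of benefit.

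**Working it through.** **The plan's own figure.** The documents give no effect, SD or power for change from nadir. The nearest figure is the primary sample size in Protocol 16.2: "Using this reduced value for SD and a treatment effect of 0.3 LogMAR in the change from baseline", where the SD of 0.55 is described thus: "this is reduced to 0.50 with the inclusion of baseline LogMAR as a covariate". With difference 0.3, SD 0.50 and two-sided 0.05, the noncentral t calculation gives 79.5% power at 44 per arm and 80.4% at 45. The stated 45 per arm is reproduced and is not in question. It was used as the arm size below.

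**One eye at a time.** Take a placebo eye going 0.8 → 1.6 → 1.3 and a treated eye steady at 0.8.
- Placebo: from baseline 1.3 − 0.8 = +0.50 (worse); from nadir 1.3 − 1.6 = −0.30, a nadir responder.
- Treated: 0 from baseline and 0 from nadir, a non-responder.

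**Arm means without noise.** Let L be the mean loss in an arm and r the fraction of it recovered by the time point, with P for placebo and G for GS010.
- Mean change from baseline = (1 − r)L.
- Mean change from nadir = −rL.
- GS010 minus placebo from nadir = r_P·L_P − r_G·L_G.

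The sign therefore depends on how much is recovered in each arm.

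**Assumed inputs, none of them in the documents.** L_P = 1.0 LogMAR, L_G = 0.5, visit-to-visit noise SD 0.10, linear fall to day 168, then recovery to day 548. From the documents: 45 per arm, baseline plus the nine visits from Visit 4 to Visit 12, and the 13.1.4 ANCOVA. Negative values favour GS010.

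| Recovery, placebo / GS010 | From baseline | From nadir, no noise | From nadir, noise SD 0.10 |
|---|---|---|---|
| 40% / 40% | 0.30 − 0.60 = −0.30 | 0.40 − 0.20 = +0.20 | +0.18 |
| 20% / 20% | 0.40 − 0.80 = −0.40 | 0.20 − 0.10 = +0.10 | +0.08 |
| 0 / 0 | 0.50 − 1.00 = −0.50 | 0 | 0.00 |
| 20% / 40% | 0.30 − 0.80 = −0.50 | 0.20 − 0.20 = 0 | 0.00 |
| 20% / 60% | 0.20 − 0.80 = −0.60 | 0.20 − 0.30 = −0.10 | −0.09 |

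**A second assumed scenario.** Placebo eyes lose 0.6 LogMAR on average (SD 0.3), GS010 prevents all of it, and noise SD runs from 0.02 to 0.10.
- All placebo eyes regain 0.3: about −0.33 from baseline; +0.25 to +0.17 from nadir, with GS010 significantly worse in 100% of simulated trials.
- Half regain 0.3: about −0.46 from baseline; +0.12 to +0.06 from nadir, significantly worse in 100% down to 51%.
- 14.7% regain 0.3 (the natural-history proportion in Protocol 6.1): −0.56 from baseline; +0.03 to −0.02 from nadir. A large benefit nearly disappears.
- None recover: −0.60 from baseline; −0.01 to −0.05 from nadir, slightly favouring GS010.

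**Noise alone.** Baseline plus nine visits is ten readings. The expected maximum of ten standard normals is 1.54, so with SD 0.10 an unchanged eye shows 1.54 × 0.10 ≈ 0.15 LogMAR of apparent improvement. About 10% of such eyes meet the rule of at least 0.3 from nadir.

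**The case against.** A reader might infer that a treatment that prevents loss must score worse than placebo on this analysis. The documents do not support that. Reversal requires placebo eyes to regain more from nadir, in absolute terms, than GS010 eyes do. With no recovery the arms tie, or differ slightly in favour of GS010. If GS010 also promotes enough recovery, the nadir comparison favours it.

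The documents point both ways on recovery. Sham eyes in REVERSE had improved by 0.246 LogMAR from baseline at Week 72 (Protocol 6.2.1), and 14.7% of natural-history eyes gained at least 15 letters (Protocol 6.1). SAP 3.4 instead describes slow untreated worsening after the initial phase and improvement on active treatment.

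Other fair points:
- Recovery is a legitimate question. Protocol 16.4.2.1 ranks the gain responder first among its three definitions. Protocol 6.2.2 reports that others have recommended treating before second-eye loss, but it does not name prevention as this trial's aim.
- The worst-of-ten inflation arises in both arms. It dilutes the contrast and does not reverse it. Gaussian noise is also a poor model for off-chart eyes, which SAP 13.1.1 assigns fixed values.
- Prevention is credited in the primary endpoint and in the stabilised-eye responder of SAP 13.2.1.

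These points limit the claim. They do not repair the test: credit given elsewhere does not make a comparison against a treatment-dependent reference a valid measure of benefit.

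**Conclusion.** The concern holds in conditional form. Change from nadir is compared between arms with the primary ANCOVA although treatment can alter the reference. Prevention of loss gets no credit, and the result can favour placebo when placebo eyes partly recover. Under the first set of assumptions the nadir difference runs from +0.18 to −0.09 LogMAR while GS010 is better by 0.30 to 0.60 from baseline. Both the sign and the size rest on recovery fractions, a loss and a noise level that the documents do not supply, so the range should be quoted, not any single value.

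The consequence is limited. This is one of the other efficacy analyses and carries no alpha. The primary endpoint and the sample size are untouched. The risk is that an unadjusted p-value is misread.

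**What to change.** In SAP 13.3:
- Report change from nadir descriptively by arm, as is already done for time to nadir, and do not interpret a between-arm p-value for it.
- For the between-arm comparison, analyse nadir LogMAR and nadir LogCS themselves at each time point with the 13.1.4 ANCOVA, adjusted for the matching baseline value. This measures depth of loss and credits prevention: with 20% recovery in both arms under the first assumptions, it gives about −0.48 LogMAR in favour of GS010.
- Keep the nadir-based responder and CRR rates, since recovery is of interest. Present them beside the from-baseline versions and state that they are not evidence of a treatment effect on their own. Deleting these models is not necessary.

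The cost is the unadjusted p-value for change from nadir and one added ANCOVA per measure. Nadir itself answers a question about depth of loss, so between-arm evidence on recovery would rest on the from-baseline measures. No new data are needed.

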### 12.5.2 Visual Acuity

Visual acuity will be assessed at each visit per the study schedule, after refraction. Eligible subjects will include those with eyes able to read letters on the Early Treatment Diabetic Retinopathy Study (ETDRS) chart, defined as on-chart eyes, and eyes unable to read letters on the ETDRS chart, defined as off-chart eyes. Please refer to the SOP for Ocular and Vision Testing for the detailed definition of off- and on-chart eyes.

On-chart eyes are able to read at least 3 letters on the ETDRS chart at 1 meter distance and will thus have an ETDRS score, Snellen BCVA and LogMAR BCVA based on the letters/lines read on the ETDRS chart at 4 and 1 meters' distance.

Off-chart subjects are not able to read at least 3 letters on the ETDRS at 1 meter distance and thus will have an ETDRS score but will not have Snellen visual acuity or LogMAR acuity obtainable based on the number of ETDRS letters/lines read. Off-chart subjects will be tested for count fingers (CF) or hand motion (HM) visual acuity per the SOP for Ocular and Vision Testing.

LogMAR visual acuity will be obtained for off-chart eyes based on Karanjia et al. 2014 (Karanjia 2014). Please see the SOP for Ocular and Vision Testing for full details. Briefly, the finger/hand dimensions of the examiner will be measured. The examiner will present the fingers/hand to assess CF or HM vision and will measure the distance at which the subject accurately counted fingers or detected HM. The finger/hand dimensions of the examiner and the distance at which CF or HM was performed will be entered into the equation utilized by Karanjia et al. 2014, modified for assessment of visual acuity in meters. The output of interest is the LogMAR BCVA.

For the purposes of the study 1 ETDRS line / 5 ETDRS letters is considered equivalent to 0.1 LogMAR and 1 ETDRS letter is equivalent to 0.02 LogMAR.

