#### *16.4.1.3 Primary Assessment Criterion*

The primary assessment criterion is the BCVA reported with LogMAR. The on-chart visual acuity (ETDRS) and off- chart visual acuity will be transformed into LogMAR according to the rules presented in the SAP.

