13.1.1. Primary efficacy variable & derivation

Visual acuity (EDTRS and LogMAR)

ETDRS score is calculated by the examiner and written on the source documents and entered in the eCRF.

One Early-Treatment Diabetic Retinopathy Study (ETDRS) line equates to 0.1 LogMAR, and 1 ETDRS letter equates to 0.02 LogMAR.

On chart and off chart

On-chart subjects are able to read at least three ETDRS letters on a single line of the ETDRS chart at 1 meter distance and will thus have an ETDRS score, Snellen visual acuity, and LogMAR visual acuity based on the letters/lines read on the ETDRS chart at 4- and 1-meter distances.

Off-chart subjects are not able to read at least three ETDRS letters on a single line of the ETDRS chart at 1 meter distance and thus will not have an ETDRS score. Off-chart subjects will be tested for count fingers (CF) or hand motion (HM) visual acuity per the SOP for Ocular and Vision Testing. The LogMAR visual acuity will be assigned to the validated Lange scale LogMAR value for CF and HM (C. Lange et al. Graefes Arch Clin Exp Ophthalmol (2009) 247:137-142):

- +2.0 LogMAR for CF
- +2.3 LogMAR for HM

For light perception (LP) +4.0 LogMAR is assigned

For no light perception (NLP) +4.5 LogMAR is assigned.

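### SAP 13.3 and SAP 13.1.1 define on-chart differently, so under letter scoring eyes at the edge of the chart can be misclassified for Clinically Relevant Recovery

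*SAP*

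**What the plan says.** SAP 13.1.1 defines the term by letters read: "On-chart subjects are able to read at least three ETDRS letters on a single line of the ETDRS chart at 1 meter distance". Such eyes have a "LogMAR visual acuity based on the letters/lines read on the ETDRS chart at 4- and 1-meter distances", and the step is given as "1 ETDRS letter equates to 0.02 LogMAR". Eyes that fail the test are assigned a value: 2.0 for count fingers (CF), 2.3 for hand motion (HM), 4.0 for light perception (LP) and 4.5 for no light perception (NLP). No starting value for on-chart eyes is given, although Protocol 16.4.1.3 says that acuities "will be transformed into LogMAR according to the rules presented in the SAP".

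SAP 13.3, inside the CRR definition, uses a LogMAR cut-off instead: "On-chart value is defined as \leq LogMAR 1.6". An eye that is on-chart at baseline needs an improvement of at least 0.2 LogMAR. An off-chart eye needs only to become on-chart. The same rules apply from nadir, and a subject has CRR if either eye does. Further down, SAP 13.3 also lists LogMAR of 1.6 or better as a separate responder endpoint, described as "equivalent to equal or better than Snellen acuity of 20/800".

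Protocol 12.5.2 has a third wording, without the single-line condition: "On-chart eyes are able to read at least 3 letters on the ETDRS chart at 1 meter distance". It adds that "1 ETDRS line / 5 ETDRS letters is considered equivalent to 0.1 LogMAR", and refers to the SOP for Ocular and Vision Testing for the detailed definition.

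The on/off-chart label is also used for the BCVA subgroups (SAP 6.4), a supportive shift table with McNemar test and candidate covariates at baseline and nadir (SAP 13.1.5), and later shift tables (SAP 13.3). None of these says which definition applies.

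**The concern.** CRR applies a different test to on-chart and off-chart eyes, so its meaning depends on where the line between them falls. If an eye has a measured chart acuity but is labelled off-chart, it can score as recovered after a change far smaller than the 0.2 LogMAR asked of other eyes with a measured acuity. In the other direction, an eye that was too poor for the chart and has come to read three letters may not be counted as recovered, although its analysed LogMAR has moved by more than 0.3.

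This would affect CRR from baseline and from nadir, at eye and subject level. If the 1.6 rule were also used for the subgroups, covariates and shift tables, those outputs would sort the same eyes differently from the definition in SAP 13.1.1.

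**Working it through.** **Inputs from the documents.** 0.02 LogMAR per letter and CF = 2.0 (SAP 13.1.1); 5 letters = 1 line = 0.1 LogMAR (Protocol 12.5.2); on-chart cut-off 1.6 and CRR gain 0.2 LogMAR (SAP 13.3).

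**Assumption, not in the documents.** LogMAR is scored letter by letter, and a fully read five-letter first line at 1 m is 1.60. This is varied in step 3.

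**Step 1: the plan's own figures.** log10(800/20) = 1.602, which rounds to 1.6, so the 20/800 equivalence reproduces. 10 letters × 0.02 = 0.20, so the CRR gain for on-chart eyes is 10 letters.

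**Step 2: classify eyes at the boundary.** For L ≥ 3 letters, LogMAR = 1.60 + 0.02 × (5 − L). Eyes with fewer than 3 letters are set to CF = 2.00. The last two columns give the smallest letter gain that scores as CRR under each rule.

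| Letters at baseline | LogMAR | SAP 13.1.1 | SAP 13.3 | Gain needed, 13.1.1 rule | Gain needed, 13.3 rule |
|---|---|---|---|---|---|
| 0 | 2.00 | off | off | 3 | 5 |
| 1 | 2.00 | off | off | 2 | 4 |
| 2 | 2.00 | off | off | 1 | 3 |
| 3 | 1.64 | on | off | 10 | 2 |
| 4 | 1.62 | on | off | 10 | 1 |
| 5 | 1.60 | on | on | 10 | 10 |

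On the analysed scale:

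- 3 to 5 letters: 1.64 − 1.60 = 0.04, a CRR under 13.3.
- 4 to 5 letters: 1.62 − 1.60 = 0.02, a CRR under 13.3.
- CF to 3 letters: 2.00 − 1.64 = 0.36. This is not a CRR under 13.3, because 1.64 exceeds 1.6. It is a Gainer under SAP 13.2.1, which asks for 0.3.
- CF to 4 letters: 2.00 − 1.62 = 0.38, with the same result.

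**Step 3: vary the missing starting value.**

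| LogMAR for 5 letters | 3 letters | 4 letters | Eyes on-chart by 13.1.1 but off-chart by 13.3 | Gain, CF to 3 letters |
|---|---|---|---|---|
| 1.56 | 1.60 | 1.58 | none | 0.40 |
| 1.58 | 1.62 | 1.60 | 3 letters | 0.38 |
| 1.60 | 1.64 | 1.62 | 3–4 letters | 0.36 |
| 1.62 | 1.66 | 1.64 | 3–5 letters | 0.34 |
| 1.64 | 1.68 | 1.66 | 3–6 letters | 0.32 |

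If three of five letters on the first line earn credit for the whole line, 3, 4 and 5 letters all score 1.6. The two definitions then coincide.

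**The case against.** **The overlap rests on a value the plan does not give.** This stands. SAP 13.1.1 refers to letters or lines, so whole-line credit is possible, and with it (or with five letters at 1.56) there is no conflict in numbers. The conflict in wording remains, and the missing conversion is itself a gap, because the protocol sends the reader to the SAP for it.

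**A small letter gain can score as CRR under SAP 13.1.1 alone.** True in letters read: moving from 2 to 3 letters is enough. On the analysed LogMAR scale it does not carry over. Under 13.1.1 an off-chart eye is assigned 2.0 or worse, so becoming on-chart is a gain of at least 0.36 with the 1.60 starting value, and of at least 0.32 across the values tried. That exceeds the 0.2 asked of on-chart eyes, so CRR stays coherent. Under 13.3 a gain of 0.02 counts and a gain of 0.36 does not.

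**SAP 13.1.1 is the general definition and the 1.6 rule sits inside CRR.** This is a natural reading, and it would leave the subgroups, covariates and shift tables untouched. The SAP does not say so, hence those outputs are only possibly affected.

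**A stronger reading concerns the primary endpoint.** A reader might infer that three letters spread over two lines score 1.64 under the protocol wording and 2.0 under the SAP, a 0.36 difference in the primary response. The documents do not support this. The SAP's primary derivation uses only 13.1.1. One SOP governs the testing. The 2.0 for count fingers belongs to the SAP, whereas Protocol 12.5.2 computes off-chart values from finger or hand size and distance. Two reading rules in actual use are not shown.

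**Conclusion.** The inconsistency is real and should be corrected before CRR is reported. SAP 13.3 classifies eyes for CRR by a rule that differs from the SAP's own definition in 13.1.1. With letter scoring and a 1.60 first line, eyes at 3–4 letters need 1–2 letters for CRR instead of 10, while count-fingers eyes that reach 3–4 letters (gain 0.36–0.38) are left out. The overlap ranges from no eyes to those reading 3–6 letters over the starting values tried, and it vanishes under whole-line credit.

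The reach is limited. CRR falls under other efficacy and has no multiplicity control (SAP 6.3). The documents do not say how many eyes lie at the boundary. The rule is the same in both arms, so no direction of bias is shown. No effect on the primary ANCOVA is shown either.

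**What to change.** In SAP 13.3, replace the LogMAR 1.6 on-chart rule with the SAP 13.1.1 definition. An eye with a measured chart LogMAR is on-chart; an eye assigned a CF, HM, LP or NLP value is off-chart. Use that single flag for CRR from baseline and nadir, the SAP 6.4 subgroups, the SAP 13.1.5 covariates and all shift and McNemar tables. Deriving the flag from measured versus assigned status avoids having to recover from a total ETDRS score whether three letters were on one line.

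State the letters-to-LogMAR conversion in SAP 13.1.1, including its starting value and whether letters or whole lines are credited. Do not hard-code 1.64 unless the stated conversion gives it. Keep LogMAR of 1.6 or better only as the separate responder threshold in SAP 13.3. Align the single-line wording between SAP 13.1.1 and Protocol 12.5.2.

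The cost is a few lines of SAP text and a little reprogramming. The downside is that CRR counts for boundary eyes will differ from those under the current rule, so the change should be recorded.
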